Protocol of a Thesis for partial fulfillment of M.D. degree of Orthopedic Surgery

4 September 2018

Title of the protocol: Functional outcome after Dual mobility cups total hip replacement versus Bipolar hemiarthroplasty in fracture neck of femur in active elderly patients.

Post graduate student: [name]

Degree: Master degree of orthopedic surgery

Director: [name] [name]

Academic position: Professor

Department: orthopedic surgery

Co-director: [name] [name]

Academic position: Assistant professor

Department: orthopedic surgery

Co-director: [name] [name]

Academic position: Lecturer

Department: orthopedic surgery

Co-director: [name] [name]

Academic position: lecturer

Department: orthopedic surgery

Co-director: [name] [name]

Academic position: Lecturer

Department: orthopedic surgery

What is already known about this subject?

What does this study add?

The decision to perform arthroplasty in patients with a femoral neck fracture is currently not well standardized. The choice between performing total hip arthroplasty or hemiarthroplasty is not straightforward in older patients with femoral neck fracture, particularly when co-morbidities are factored in.⁽¹⁾ This led us to carry out this comparative study between Dual mobility cups total hip replacement and bipolar hemiarthroplasty to reveal the functional and mechanical outcome of each.

1. Introduction/Review

Femoral neck fractures in the elderly are frequent, represent a great health care problem, and have a significant impact on health insurance costs.⁽²⁾ A typical patient with fracture neck of femur is characterized by old age, severe osteoporosis and significant co-morbid diseases. Fracture neck of femur has always been a great challenge to the orthopedic surgeon.⁽³⁾

The primary aim of treatment should be to perform a surgery that provides the patient with the greatest opportunity for early ambulation. This requirement is fulfilled to a great extent by the use of a primary prosthetic replacement.

Reconstruction options using hip arthroplasty include bipolar hemiarthroplasty (HA), and total hip arthroplasty (THA) & Dual mobility cups total hip replacement (DMTHA).⁽⁴⁾

Bipolar hemiarthroplasty (HA) has long been the preferred treatment, and is performed in 75% of cases. It is justified by the reasonable operating time, low blood loss and acceptable functional outcomes. In the 2000s, total hip arthroplasty (THA) emerged as a relevant alternative to HA. Since then, there is an on-going debate on the best implant to use. Age, co-morbidities, patient independence and potential surgical complications must be taken into account when deciding between implants.⁽⁵⁾ The risk of dislocation is a key deciding factor because of its well-described consequences. Up to the early 2010s, the THA procedures described in the studies used a fixed cup. In some cases, this

resulted in the dislocation rate being higher than with HA. The emergence of dual mobility (DM) cups has reduced the dislocation rate.⁽⁶⁾ However, the relative role of DMTHA and HA is not well defined in the context of co-morbidities and functional outcome.⁽⁷⁾

2.Aim/Objectives

The aim of the work is to compare the results of the functional outcome, mechanical outcome and the possible complications of bipolar hemiarthroplasty versus dual mobility cups total hip replacement in fracture neck of femur in active elderly patients.

3.Methodology

- **Type of the study:** randomized control clinical trial
- **Study setting:** Ain Shams University hospitals
- **Study period:** 24 months
- **Study population:** active elderly patients with fracture neck of femur

Inclusion criteria:

- Sex: both sexes
- Age: 60-80 years old
- Lesion: displaced fracture neck of femur

Exclusion criteria:

- Acetabular grade 3 arthritis
- Acetabular dysplasia
- Previous hip surgeries

- **Sampling method:** convenient sample

- **Sample size:** 30 patients will be randomly divided by a computer generated sequence in to 2 groups:

- Group A: will undergo bipolar hemiarthroplasty
- Group B: will undergo dual mobility cups total hip replacement.

- **Ethical considerations:** will be followed by obtaining the hospital research/ethics committee approval and written informed consents from the patients.
- **Study tools:**
 - **Preoperative diagnosis and evaluation:**
 - **Clinical Evaluation:**
 - **History:** Katz index of independence in activity of daily living (ADL) will be used to estimate the independence of patients immediately before their fracture occurred.
 - **General examination**
 - **Local examination**
 - **Radiological Evaluation:**
 - Plain X-ray Pelvis showing both hips (antero-posterior)
 - Plain X-ray of the fractured hip showing the femur (antero-posterior & lateral).
 - **Laboratory investigations:** CBC & routine preoperative lab investigations
 - **Operative technique:**
All the patients will be operated through the standard posterior approach, intra-osseous repair of the capsule and the lateral rotators will be done in all cases.
Blood loss, the need for blood transfusion and the operative time will be recorded.
 - **Post-operative management:**
 - Proper antibiotic and analgesics will be given post-operative.
 - Prophylaxis against DVT
 - Post-operative x-rays will be done, plain X-ray pelvis showing both hips (antero-posterior view) & plain X-ray of the operated hip showing femur (antero-posterior view).
 - **Follow up strategy:**
Patients will be reviewed after 2 weeks to check their wounds and for sutures removal, then the follow up will be every month in the first 6 months then every 3 months till the end of the study (2 years). The follow up will include:

➤ **Clinical and functional assessment:**

- Harris hip score to assess the function.
- Visual analogue scale (VAS) to assess pain.
- Emotional acceptance.
- Walking ability and the use of walking aids.
- Gait.

➤ **Radiological assessment:**

Plain X-ray as described before at every follow up visit.

- **Statistical Analysis:** Statistical package for social science (SPSS 15.0.1 for windows; SPSS Inc., Chicago, IL, 2001). Data will be presented as Mean and Standard deviation (+/-SD) for quantitative parametric data, and Median and Interquartile range for quantitative non parametric data. Frequency and percentage will be used for presenting qualitative data. Suitable analysis will be done according to the type of data obtained. P<0.05 will be considered significant.
- **Statistical package:** data entry and statistical analysis of the collected data will be performed using a reliable software program.

4. References

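### No primary outcome, visit or test is fixed and P<0.05 is unrestricted, so for scored measures the false-positive chance passes 5% once two tests can count

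*Combined protocol and SAP*

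**What the plan says.** The inferential plan in section 3 (Methodology), Statistical Analysis, is: "Suitable analysis will be done according to the type of data obtained. P<0.05 will be considered significant". The rest of that entry covers software and descriptive summaries.

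The other relevant text is spread over the document:

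- **Title:** "Functional outcome after Dual mobility cups total hip replacement versus Bipolar hemiarthroplasty".
- **What does this study add?** The comparison is meant "to reveal the functional and mechanical outcome of each".
- **Section 2, Aim/Objectives:** the aim is to "compare the results of the functional outcome, mechanical outcome and the possible complications" of the two procedures. The three domains are not ranked.
- **Section 3, Follow up strategy:** the list opens with "Harris hip score to assess the function", followed by VAS pain, emotional acceptance, walking ability and aids, and gait, with X-rays as well. After a 2-week wound check, visits are "every month in the first 6 months then every 3 months till the end of the study (2 years").
- **Section 3, Operative technique:** "Blood loss, the need for blood transfusion and the operative time will be recorded".
- **Section 3:** "Study period: 24 months".

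Nowhere is an outcome designated primary, a visit chosen for the comparison, a multiplicity rule given or an outcome labelled exploratory.

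**The concern.** A 5% threshold limits the false-positive chance of one test. It limits that of the trial only if the plan says which test carries the conclusion. Here the threshold applies to every result, and the test itself is to be chosen once the data are in hand. Followed as written, the plan lets an implant difference be called significant on whichever outcome or visit falls below 0.05. A reader of the report could not tell whether that comparison was chosen before or after the results were seen. This cannot be put right credibly once outcomes are known.

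**Working it through.** **Inputs from the document**

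- Per-test threshold: 0.05. Sidedness is not stated; two-sided is assumed.
- Patients: 30 in total. No allocation ratio is given; 15 per arm is assumed.
- Clinical items: 5 (Harris, VAS, emotional acceptance, walking, gait).
- Visits after the wound check: months 1 to 6 give 6; months 9, 12, 15, 18, 21 and 24 give (24 − 6)/3 = 6; total 12.
- Operative measures: 3 (blood loss, transfusion, operative time).

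**Assumptions not in the document**

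Complete data, correlation between visits 0.6-0.9, correlation between items 0.3-0.7, and no true difference on any measure.

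**Step 1. The plan's own error rate.** With one test, 1 − 0.95 = 5%. In the simulations below, each single t test rejected 4.95-5.15% of the time, so the set-up reproduces the stated level.

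**Step 2. Independent tests, as a reference.** The chance of at least one P<0.05 among k tests is 1 − 0.95^k:

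- k = 2: 1 − 0.9025 = 9.75%
- k = 5: 1 − 0.7738 = 22.6%

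**Step 3. Correlated scored measures.** Repeated scores in the same patients are not independent, so the independent figures are too high. Simulation from a multivariate normal distribution with constant correlation (15 per arm, two-sided t tests at 0.05, 60,000 replicates, Monte Carlo standard error at most 0.24 points) gives:

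| Tests that can count | Lower correlation | Higher correlation |
|---|---|---|
| Harris at 2 visits (r 0.6 / 0.9) | 8.79% | 7.01% |
| Harris at 3 visits (r 0.6 / 0.9) | 12.07% | 8.51% |
| Harris and VAS, one visit (r 0.3 / 0.7) | 9.45% | 8.51% |
| Five items by t test, one visit (r 0.3 / 0.7) | 21.09% | 15.53% |

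A separate run gave 8.2-9.4% for Harris and VAS, so that row is best read as 8-9%. With 10 or 12 per arm, the two-visit figure is 7.1-8.9% and the five-item figure 15.4-21.3%, so the 15-per-arm assumption matters little.

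**Step 4. Binary items.** Fisher's exact test is conservative at this size. Enumerating all tables at 15 v 15, its true error rate at event rates of 5, 10, 20, 30 and 50% is 0.06, 0.55, 1.67, 1.70 and 1.65%. Two independent tests give at most 1 − (1 − 0.017)² = 3.4%, which is below 5%. Three give 1 − 0.983³ = 5.0%. A mixed set still exceeds 5%: if three of the five items are yes/no and tested by Fisher while two are scored, the total is 8.8-13.9%.

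**Step 5. The unnamed test.** Taking the better of a t test and a Mann-Whitney test on one outcome at one visit gives about 5.7%. In these calculations the open choice of outcome and visit adds more than the open choice of test.

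**Step 6. A single comparison.** One t test on one fixed outcome returns the rate to 5%. Even a single test of the Harris score averaged over all 12 visits stays at 4.95-5.16%. The excess comes from the number of tests that can count, not from the number of visits.

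**The case against.** **The Harris score is already the implied primary.** The title speaks of functional outcome, and the Harris score is the one item listed for function, in first place. It is the natural lead, and this narrows the choice. But it is not designated, it has no visit and no test, and both the background and the aim set mechanical outcome beside function. Granting Harris still leaves about 12 candidate visits.

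**More than one test does not always mean more than 5%.** A reader might infer that any second test breaches the limit. Step 4 shows that this is wrong for two binary items tested exactly, and the plan does expect qualitative data. This objection stands, and the point is therefore confined to tests that run at their nominal level, as t tests on Harris and VAS would.

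**The schedule is not a list of tests.** A reader might infer from five items and 12 visits that 60 tests are planned, or that Harris will be tested separately at each visit. The document says what is assessed at follow-up, not what is tested or when. Separate Harris tests at all 12 visits would give 14.09-28.38% with constant correlation, but this is hypothetical. Complete follow-up is also uncertain: if the 24-month study period includes recruitment, late entrants cannot reach every visit. The point does not rest on that range.

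**This is a small thesis comparison with no stated hypothesis.** Strict error control over every outcome is not clearly owed. That is fair, and none is asked for here. But the plan does adopt a significance threshold, and so needs to say which comparison it governs.

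**Conclusion.** The concern holds in this limited form. The plan fixes no primary outcome, visit, test or hierarchy, and its one threshold is unrestricted. For scored measures, two tests that can count raise the false-positive chance from 5% to about 7-9% (Harris at two visits) or 8-9% (Harris and VAS at one visit). Five items by t test raise it to 16-21%. The percentages depend on the assumed correlations, 15 per arm and complete data; the omission itself does not.

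The documents do not show how many tests are intended, and they do not show that anyone means to select a favourable result. What they show is that nothing would prevent it or reveal it. The case for changing the plan rests on the missing designation, not on the larger hypothetical percentages. It should be settled before the results are analysed.

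**What to change.** Before outcome data are seen, add to Statistical Analysis:

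*The primary outcome is the Harris hip score at [one named visit], compared between the randomised groups by a two-sided Welch t test at 0.05 and reported as a mean difference with 95% confidence interval. All other outcomes (VAS, emotional acceptance, walking, gait, operative measures, radiological findings, complications) and all other visits are secondary or exploratory. They are reported with 95% confidence intervals and not as confirmatory findings.*

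The visit must be one that every patient reaches within the 24-month study period. That period and the 2-year follow-up have to be reconciled first, so the sponsor must name the visit. The document is dated 4 September 2018 and does not show whether outcomes have since been seen; if they have, the report should say that the primary comparison was chosen afterwards.

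The cost is one decision about the timetable and a few sentences, with no added patients, visits or measurements. The downside is that differences in other outcomes, or at other visits, can no longer be presented as confirmatory.
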